9.2. Analysis of Secondary Efficacy Endpoints

The secondary efficacy endpoints are including the following:

- Improvements (from baseline to Day 85 and Day 169) in the SLEDAI-2K, BILAG-2004, PGA, and FACIT-Fatigue scores
- Improvements in tender or swollen joint count (from baseline to Day 85 and Day 169)
- Reduction in oral steroids at Day 169 relative to Day 85
- The proportion of subjects achieving a 50% improvement in CLASI Activity score (from baseline to Day 85 and Day 169)

9.2.1. SLEDAI-2K

Systemic Lupus Erythematosus Disease Activity Index SELENA Modification will be performed for each subject at scheduled visits to determine the SLE disease activity for each subject at the visit. The total score (defined as the sum of weights next to descriptors marked present) will be summarized. The improvements from Baseline (Day 1) to Day 85 and from Baseline (Day 1) to Day 169 in SLEDAI-2K total scores will be evaluated as part of the secondary efficacy endpoints. Lower score represents less disease activity.

Summary of observed values: Observed values of total score and the change from baseline at each scheduled visit will be summarized. In addition to the LOCF imputation described below, the change from Baseline on observed values will be analyzed using Mixed effect Model Repeat Measurement (MMRM) method as described in the SAP Section 9.1.

Summary of imputed values: Imputed values and the change from Baseline (Day 1) in the SLEDAI-2K total score at each scheduled visit will also be analyzed. The two-sample t-test will be used for the treatment group comparison on the change from Baseline. LOCF will be used to impute missing values on the FAS.

9.2.2. BILAG-2004

BILAG-2004 Index Assessment will be performed for each subject at scheduled visits to determine the SLE disease activity for each subject at the visit. The assessment includes subsections of Constitutional, Mucocutaneous, Neuropsychiatry, Musculoskeletal, Cardiorespiratory, Gastrointestinal, Ophthalmic, Renal and Hematological. Each subsection will be scored with Category of Zero or Non-Zero for analysis. Any category checked other than “Not Present” or “Not Done” will be treated as the Non-Zero category except for the Renal and Hematology panels. The category of Zero or Non-Zero will be presented in the summary. The improvements from Baseline (Day 1) to Day 85 and from Baseline (Day 1) to Day 169 in BILAG-2004 Index Assessment category of Zero or Non-Zero will be evaluated as part of the

secondary efficacy endpoints. Zero category represents no disease activity present for the body system. The detailed specifications of Zero or Non-Zero category rules for the Renal and Hematology panels will be stated in the analysis dataset specification document rather than in this SAP”.

Summary of observed values: Observed values of the Zero and Non-Zero categories and the change from baseline at each scheduled visit (indicated by a shift from the baseline category) will be summarized for each subsection. The percentages will be calculated based on the actual number of subjects at each visit in each treatment group of the FAS. No statistical testing will be performed.

Summary of imputed values: Imputed values of the Zero and Non-Zero categories and the change from Baseline (Day 1) for the BILAG-2004 Index Assessment at each scheduled visit (indicated by a shift from the baseline category) will be summarized for each subsection. LOCF will be used to impute missing values on the FAS. No statistical testing will be performed.

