### 6.1 Subject Inclusion Criteria

Subjects who meet the following criteria may be included in the study:

1. diagnosis of SLE by meeting four of the eleven ACR criteria described in the 1997 update of the 1982 SLE criteria (see Appendix D) including cutaneous involvement at Screening;
2. cutaneous manifestations of SLE and a CLASI activity score of  $\geq 10$  at Screening;
3. elevated levels of any one of the following autoantibodies (local or central laboratory):
  - Ro-52/60, La, Sm, SmRNP, U1 RNP A/68;
4. no changes to SLE medications in the 30 days prior to Baseline;
5. able to communicate and able to provide valid, written informed consent;
6. ages 18 to 70 inclusive;
7. minimum weight of 45 kg;
8. Female participants shall be either of non-child-bearing potential (permanently sterilized by tubal occlusion, hysterectomy, or bilateral salpingectomy, or menopausal more than one year since last menstrual cycle and confirmed by ensuring blood FSH levels  $\geq 22$  mIU/mL); OR practicing highly effective contraception (e.g., oral, implantable, transdermal or injectable contraceptives, a non-hormonal intrauterine device [IUD] with spermicide; female condom with spermicide; contraceptive sponge with spermicide; intravaginal system, diaphragm with spermicide; cervical cap with spermicide; a male sexual partner who agrees to use a male condom with spermicide; a sterile sexual partner) for at least 2 months prior to dosing and until 110 days following the End of Study.
9. Male participants must agree to use a male condom with spermicide from the first dose until 90 days after the last dose. Male participants must agree not to donate sperm from the first dose until 90 days after the last dose.

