### 11.3 Analysis of the Secondary Objectives

The following secondary objectives will be compared between the two treatment arms:

- The immunogenicity of RSLV-132 as measured by the presence of RSLV-132 antibodies
- Improvements (from Baseline to Day 85 and Day 169) in the SLEDAI-2K, PGA, and BILAG-2004 scores
- Improvement (from Baseline to Day 85 and Day 169) in the FACIT-Fatigue scale
- Improvements (from Baseline to Day 85 and Day 169) in tender or swollen joint count
- Reduction in oral steroids at Day 169 relative to Day 85
- The proportion of subjects achieving a 50% improvement in CLASI activity score

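### BILAG-2004 is analysed only as Zero or Non-Zero per subsection, so partial improvement or worsening of activity already present at Baseline cannot appear

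*SAP*

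**What the plan says.** Protocol 11.3 lists among the secondary comparisons "Improvements (from Baseline to Day 85 and Day 169) in the SLEDAI-2K, PGA, and BILAG-2004 scores". It does not define a BILAG-2004 score, and Protocol section 11 leaves analysis detail to the SAP.

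SAP 9.2.2 supplies the definition. For the nine subsections, "Each subsection will be scored with Category of Zero or Non-Zero for analysis", and "Zero category represents no disease activity present for the body system". Any checked category other than *Not Present* or *Not Done* "will be treated as the Non-Zero category except for the Renal and Hematology panels". For those two panels the rules "will be stated in the analysis dataset specification document rather than in this SAP", although they too end in Zero or Non-Zero. Change from Baseline is the shift between categories, tabulated per subsection on observed values and again on imputed values. For the imputed values the SAP adds: "LOCF will be used to impute missing values on the FAS. No statistical testing will be performed". The observed values are not tested either. No graded or numeric BILAG-2004 summary is planned.

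Protocol 6.1 requires "cutaneous manifestations of SLE and a CLASI activity score of" at least 10 at Screening. Protocol 6.2 has an adjudicator confirm this from photographs, and Protocol 12.3 re-evaluates the CLASI score before the first dose.

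**The concern.** The trial selects patients for active skin disease and then analyses one of its organ-system instruments on a scale with a single active level. In a subsection where a subject starts active, that scale has no room above the starting point and only one step below it. The endpoint is named as improvement, but improvement short of clearance is not counted.

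What is at stake is how much this endpoint can contribute. SAP section 5 says the analysis will look for trends in the data summaries. With no test on BILAG-2004, the shift table is the whole of the planned evidence from the instrument, and its resolution sets what can be learned. Worsening matters as well: under Protocol 7.4 steroid reductions begin at Day 85 in subjects with a 50% CLASI response, so a change in already active disease between Days 85 and 169 is of interest. SLEDAI-2K and PGA keep a numeric score in the SAP, while BILAG-2004 is collapsed.

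**Working it through.** The documents give no BILAG-2004 rate, effect size or power figure, so there is nothing to reproduce. The check is of the scoring logic.

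**Inputs.** Two analysis categories and a shift from Baseline (SAP 9.2.2); CLASI activity of at least 10 at entry (Protocol 6.1); 50% CLASI improvement as the responder criterion (SAP 9.2.7); approximately 50 subjects randomized 2:1 (SAP 2.3.1). The number k of ordered active levels in a subsection is my assumption, because the documents do not list the BILAG-2004 categories or grades.

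**1. Baseline status in Mucocutaneous.** A subject with CLASI activity of at least 10 should have at least one mucocutaneous item recorded as active, hence Non-Zero. This is inferred; the documents do not show how CLASI lesions map to BILAG-2004 items.

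**2. What the shift can register.**

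| Baseline | True course | Planned table shows |
|---|---|---|
| Non-Zero | complete clearance | shift to Zero |
| Non-Zero | partial improvement | no shift |
| Non-Zero | unchanged | no shift |
| Non-Zero | worsening | no shift |
| Zero | new activity | shift to Non-Zero |
| Zero | remains inactive | no shift |

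**3. Counting the hidden moves.** From k active starting levels to k + 1 possible end levels there are k(k + 1) pairs: k moves to Zero, k unchanged, k(k − 1)/2 partial improvements and k(k − 1)/2 worsenings.

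- k = 2: 6 pairs = 2 to Zero + 2 unchanged + 1 partial improvement + 1 worsening
- k = 3: 12 = 3 + 3 + 3 + 3
- k = 4: 20 = 4 + 4 + 6 + 6

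For every k the table registers the k moves to Zero and none of the partial improvements or worsenings.

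**4. Against the trial's own responder criterion.** Take a subject whose CLASI activity falls from 20 to 4: (20 − 4)/20 = 80%, well beyond 50%. If any mucocutaneous item is still recorded as active, BILAG-2004 shows no shift.

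**5. How thin the informative cell may be.** The 2:1 split of 50 is 50 × 2/3 = 33.3 and 50 × 1/3 = 16.7, so about 33 and 17. Suppose complete mucocutaneous clearance occurs in 5% on placebo and in 10%, 20% or 30% on RSLV-132 (assumed rates, for illustration only). Expected counts cleared are 33 × 0.10 = 3.3, 33 × 0.20 = 6.6 or 33 × 0.30 = 9.9, against 17 × 0.05 = 0.85. All other subjects who start active fall in one undifferentiated cell.

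**6. A qualifier on clearance.** SAP 9.2.2 keeps *Not Done* out of Non-Zero but does not say whether it is Zero or missing. If it were coded Zero, a subsection left unassessed at a later visit could appear as clearance, although the SAP defines Zero as absence of disease activity.

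**7. What other endpoints cover.** CLASI activity is analysed as change and percent change at each visit (SAP 9.1), joint count as change from Baseline (9.2.5), PGA on a 0 to 100 mm scale (9.2.3) and SLEDAI-2K as a total (9.2.1). The SLEDAI-2K total sums weights for descriptors present, so it does not grade partial change within a descriptor. BILAG-2004 is the only instrument tabulated by organ system.

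**The case against.** The best defence is that little depends on this table. BILAG-2004 is one of several secondary endpoints, is untested, and feeds no decision rule. Skin, the system for which patients were selected, is measured in detail by the primary endpoint, so the fall from 20 to 4 is fully captured there; joints and global activity have their own graded measures. All data will be listed (SAP section 9). Zero or Non-Zero is a prespecified coding whose meaning the SAP states. This stands, and it limits the impact to moderate. It does not give the BILAG-2004 table any resolution in active subsections, nor does it supply a graded clinical index by system outside skin and joints.

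Stronger readings are tempting, and the documents do not support them:

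- A reader might infer that worsening joints can never show. Entry does not require joint disease. A subject who is Zero in Musculoskeletal at Baseline and develops activity shifts to Non-Zero; only subjects already active there are affected.
- A reader might infer that the trial as a whole hides worsening. The limit lies within the BILAG-2004 table.
- A reader might infer that the SAP contradicts the protocol. The protocol names scores without defining them and defers detail to the SAP. This is a weak analysis choice.
- A reader might infer that a flat table will be taken as evidence of no effect. Nothing in the documents says so.

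**Conclusion.** The point holds within these bounds. In any subsection that is Non-Zero at Baseline, the planned analysis can show complete clearance and nothing else; partial improvement and worsening of existing activity are invisible by construction. That follows from SAP 9.2.2 alone and does not depend on the assumed k or clearance rates. The main effect is in one of the nine subsections, Mucocutaneous, where nearly all of about 50 subjects should start Non-Zero. That rests on inference from the CLASI entry criterion and could not be checked against the BILAG-2004 form. Elsewhere the effect is confined to subjects active at Baseline, whose number the documents do not give. The impact is moderate: the change is worth making because a named secondary endpoint is otherwise nearly uninformative where disease is most active, but the primary analysis and the other graded endpoints are untouched.

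**What to change.** Keep the Zero/Non-Zero table and add to SAP 9.2.2:

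- For each subsection, by arm at Days 85 and 169, the number and percentage improved, unchanged and worsened from Baseline, based on the BILAG-2004 subsection grade derived from the recorded items with the instrument's own scoring rules. Report improvement among subjects active in that subsection at Baseline.
- A reference in the SAP to the scoring algorithm, including Renal and Hematology, whose rules now sit in a separate specification. The algorithm is not in either document, so the team should confirm that the CRF holds every item it needs. Taking the worst checked item category as a shortcut is not advised, since the documents give no severity ordering of the categories.
- A statement that *Not Done* is treated as missing and not as Zero.

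Fix the rule before unblinding. If unblinding has already occurred, label the added summary post hoc.

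The cost is a short SAP addition, some programming and one more descriptive table. No new assessment is needed: Protocol Appendix A already schedules BILAG-2004 at Baseline and at six later visits (Days 29, 57, 85, 113, 141 and 169).

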3.2.5. Missing Data and Outliers

Every attempt will be made to capture all study data. For subjects whose visit value is missing, the last observation will be carried forward (LOCF) for the efficacy analyses. Any missing, unused, or spurious data will be noted in the final CSR.

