3.2.7. Study Baseline and Study Day

Baseline is defined as the last assessment prior to the first dose of study drug (RSLV-132 or Placebo) at Day 1. Measurements that are obtained after the first dose of study drug will be considered post-baseline values. Change from baseline is defined as post-baseline assessment minus baseline assessment.

Study day for events on or after the date of the first dose will be defined as the number of days from the date of the first dose of study drug, plus 1 day, so that the date of the first dose will be defined as Day 1. For events before the date of the first dose, study day will be calculated as the difference in days between the date of the first dose and the date of interest. Thus, the day before the date of the first dose will be defined as Day -1.

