9. EFFICACY ANALYSES

Efficacy analyses include assessing improvement in disease activity using CLASI, SLEDAI-2K, BILAG-2004, PGA, and FACIT-Fatigue scores; tender or swollen joint count; oral steroids use; as well as evaluating the autoantibody and complement profiles.

Each assessment will be summarized descriptively by treatment group on the FAS for all study visits at which the data were collected. No statistical testing will be performed, unless otherwise specified.

All data will be listed.

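### SAP 9.2.2 does not say that an unassessed BILAG-2004 subsection is missing; its two-level score most naturally codes it as Zero, meaning no disease activity

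*SAP*

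**What the plan says.** SAP 9.2.2 lists nine BILAG-2004 subsections and reduces each to two levels: "Each subsection will be scored with Category of Zero or Non-Zero for analysis". Non-Zero is defined by exclusion: "Any category checked other than “Not Present” or “Not Done” will be treated as the Non-Zero category except for the Renal and Hematology panels". The rules for Renal and Hematology are left to the analysis dataset specification. The meaning of the other level is given separately: "Zero category represents no disease activity present for the body system".

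Observed values are summarised as category counts and shifts from baseline, and "The percentages will be calculated based on the actual number of subjects at each visit in each treatment group of the FAS". The imputed summary adds "LOCF will be used to impute missing values on the FAS". The general rule in SAP 3.2.5 is "For subjects whose visit value is missing, the last observation will be carried forward (LOCF) for the efficacy analyses". Neither sentence mentions 'Not Done'. No statistical test is planned on either BILAG summary.

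SAP 3.2.7 sets the reference value: "Baseline is defined as the last assessment prior to the first dose of study drug". Protocol 12.3, 12.5 and Appendix A schedule BILAG at baseline and on Days 29, 57, 85, 113, 141 and 169. It is not scheduled at Screening.

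**The concern.** 'Not Done' and 'Not Present' carry different information: one says the feature was not assessed, the other that it was assessed and absent. The scoring rule treats them alike, and the score has no third level. A programmer who follows the text would most naturally put a wholly unassessed subsection in Zero.

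Three distortions could follow:

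- A subsection active at baseline and unassessed at Day 85 or Day 169 would appear as a shift to Zero, that is, an improvement.
- A subsection unassessed at baseline and active later would appear as a worsening.
- LOCF would repair neither case, because the visit already holds a category, and it could carry a false Zero to later visits.

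The unassessed subject would also stay in the denominator of the observed percentages. Improvement in BILAG-2004 at Days 85 and 169 is a named secondary endpoint, and Zero/Non-Zero is the only BILAG summary planned. SAP section 5 says the analysis will look for trends in the summaries, so the tables themselves have to be right.

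**Working it through.** The plan gives no figure on this point to reproduce. The check has three parts.

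**1. Apply the rule to the possible entries.** SAP 9.2.2 names 9 subsections. It excepts 2 (Renal and Hematological), so the rule covers 9 − 2 = 7.

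| Entries in the subsection | Result under 9.2.2 |
|---|---|
| All 'Not Present' | Zero |
| 'Not Present' with some 'Not Done' | Zero, by elimination |
| All 'Not Done' | Zero, by elimination |
| Any active entry, with or without 'Not Done' | Non-Zero |

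The first and third rows get the same score, although nothing was assessed in the third.

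**2. Effect of one subject.** Inputs: about 50 subjects randomised 2:1 (Protocol synopsis and 5.1; SAP 2.3.1). Assumption: a 33:17 split, with everyone attending the visit.

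- One truly Non-Zero subject scored Zero moves the subsection percentage by 1/n. RSLV-132: 1/33 = 3.0 points. Placebo: 1/17 = 5.9 points.
- The alternative is to score that subject missing and remove them from the denominator. If z of n subjects are scored Zero and one of these was unassessed, the overstatement is z/n − (z−1)/(n−1) = (n−z)/(n(n−1)).

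| Arm | z = 1 | About half Zero | All Zero |
|---|---|---|---|
| RSLV-132, n = 33 | 32/(33×32) = 3.0 points | z = 17: 16/(33×32) = 1.5 points | 0 |
| Placebo, n = 17 | 16/(17×16) = 5.9 points | z = 9: 8/(17×16) = 2.9 points | 0 |

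**3. How far one entry can spread.** There are 6 post-baseline BILAG visits. A false Zero at baseline is the reference for all 6 shift rows of that subsection, including both endpoint visits. A false Zero at a subject's last BILAG visit on Day 85 would be carried by LOCF to 3 more visits (Days 113, 141 and 169).

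The documents give no frequency for 'Not Done', so no expected number of affected subjects can be derived.

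**The case against.** The strongest reply is that the SAP defines only Non-Zero. It does not say that everything else is Zero, and a subsection nobody assessed does not meet the description of Zero as absence of activity. The LOCF sentence in 9.2.2 also presupposes that some values are missing. On that reading a wholly 'Not Done' subsection is missing, and the false shift, the carry-forward and the denominator effect all disappear. The denominator wording could likewise mean subjects with a value for that subsection.

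This stands in part: the SAP allows that reading. It does not state it, though, and two programmers could produce different tables from the same text. For FACIT-Fatigue, by contrast, SAP 9.2.4 spells out what to do with unanswered items (prorate when at least 7 of 13 are answered). BILAG has no equivalent, and the dataset specification is promised only for Renal and Hematology.

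Other points on this side also stand. SAP section 9 says "All data will be listed", and SAP 3.2.5 says missing data will be noted in the study report, so raw 'Not Done' entries would remain visible, although the tables would not be corrected. Protocol 12.10 asks for experienced rheumatologists as assessors. The BILAG form is not reproduced, so it is unknown whether 'Not Done' is offered per item or per panel.

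A reader might infer that the comparison between arms is biased. The documents do not support that: assessors are blinded, and nothing points to 'Not Done' being more frequent in one arm.

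**Conclusion.** The point holds as a scoring rule whose most natural reading gives a wrong result for a subsection with no assessed item, in seven of nine subsections. It should not be put as a statement by the SAP that 'Not Done' equals Zero; that sentence is not there, and the conclusion is reached by elimination.

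The size is 3.0 points (RSLV-132) or 5.9 points (placebo) per truly active subject scored Zero. Compared with treating the subject as missing, the overstatement of the Zero percentage lies between 0 and those same values. These figures assume a 33:17 split with full attendance; withdrawals, who are not replaced, would make the arms smaller and each subject's weight larger.

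The weight is limited. This is one secondary endpoint, descriptive and untested, in a study with no formal hypothesis testing. The primary CLASI endpoint is untouched. The change is worth making before database lock because it is cheap and removes an ambiguity from the only planned BILAG tables.

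**What to change.** In SAP 9.2.2:

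- State that 'Not Done' is missing, not Zero.
- Score a subsection Non-Zero if any assessed entry is active, and missing if nothing in it was assessed.
- Choose and prespecify one rule for inactive subsections that were only partly assessed. The choice is the sponsor's, since the form is not in the documents.
- Exclude missing subsections from the observed-value denominator; LOCF then applies to them in the imputed summary.
- Report 'Not Done' counts by arm and visit.

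Apply the same principle to Renal and Hematology in the dataset specification.

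The cost is a few sentences and a little programming. The downside is some additional missing values, in a number the documents do not allow to be estimated. A missing baseline cannot be recovered, because BILAG is not done at Screening, so that subject drops out of all six shift rows for the subsection. LOCF may also carry forward an earlier Non-Zero where activity had in fact resolved; the 'Not Done' counts would show how much room there is for this.
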